A Phase 2, Prospective, Randomized,
Multicenter, Open-Label, Controlled Trial
to Assess to the Efficacy and Safety of
Exenatide SR for the prevention of
diabetes after kidney transplantation

NCT03961256

2/19/2020

Name of Investigational Product: Exenatide SR

Title of Study: A Phase 2, Prospective, Randomized, Multicenter, Open-Label, Controlled Trial to Assess to the Efficacy and Safety of Exenatide SR for the prevention of diabetes after kidney transplantation.

Version 2.0 dated February 19, 2020

Lead Investigator: [name]., Mayo Clinic, Rochester, MN

Study hypothesis

In renal transplant recipients who have prediabetes as determined by 4 or 12 months after kidney transplantation, treatment with the GLP-1 receptor agonist - Exenatide SR + standard-of-care (SOC) vs. SOC alone will reduce the incidence of diabetes at 24 months after kidney transplantation.

Intervention group

Patients randomized to the intervention group will, in addition to standard care, receive Exenatide SR 2 mg SQ weekly at the time of randomization and continue until 24 months post transplant. The decision to continue beyond 24 months of follow-up will be left to the discretion of the caring physician.

Standard care

Participants randomized to the standard care group will receive standard post-transplant care as per Mayo Clinic usual practice. Standard immunosuppression includes a tacrolimus, mycophenolate with/without prednisone as per Mayo Clinic immunosuppression protocols.

The current lifestyle standard care after kidney transplantation at Mayo Clinic hospital includes advice for regular exercise and a nutritional assessment. The nutrition care involves giving patients resources guiding them on healthy eating and food safety after transplant.

Study objectives.

Primary:

To compare the rate of progression from prediabetes at 4 months or 12 months to frank diabetes at 24 months (as defined by increase in HbA1C or fasting BS to diabetic range based on the ADA criteria) after transplantation in kidney transplant recipients on Exenatide SR + SOC vs. standard-of-care alone in a multicenter randomized study.

Secondary:

- To evaluate the rate of progression to diabetes by 24 months after transplantation
- To evaluate the safety and tolerability of Exenatide SR
- To compare hemoglobin A1c levels in patients treated with Exenatide SR + SOC vs. SOC alone at 24 months after kidney transplantation.

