This is a Phase 2, Prospective, Randomized, Multicenter, Open-Label, Controlled Trial. Patients are randomized to treatment with Exenatide SR + SOC vs. SOC alone at 4 months or 12 months post transplant after kidney transplantation and followed until 24 months after kidney transplantation. Patients who discontinued medication for AEs will be contacted within 30 days to follow up on the resolution of symptoms.

Study participants with prediabetes at 4 months or 12 months after kidney transplantation will be randomized 2:1 to receive either Exenatide SR or diet and exercise only with no medication. We plan to enroll approximately 50% of subjects at 4 months post transplant and 50% of subjects at 12 months post transplant

Primary Endpoint is the incidence of diabetes at 24 months after kidney transplantation.

Patients will be followed for 2 years after transplantation (20 or 12 months after enrollment) for progression to all endpoints. Therefore, there will be three SOC biopsies—4, 12 and 24 months after transplantation. Hemoglobin A1C will be performed at the same time points. In addition 2hOGTT will be performed if clinically indicated per our SOC.

Study Sites: This is a multicenter study involving the three Mayo Clinic kidney transplant programs. This group has a common IRB and can contract centrally. Collectively, they perform approximately 600 kidney transplants per year. They have a history of multicenter research trials—they enrolled 480 patients along with a fourth center in a recent NIH-sponsored trial that required a 1 year kidney biopsy (NCT01782586 Validation of Gene Expression Markers of Renal Allograft Functional Decline (<https://clinicaltrials.gov/ct2/show/NCT01782586?term=[name]&rank=10>)). Thus, this consortium is large enough to ensure enrollment in the time frame suggested, yet small enough to ensure collaboration and uniformity needed for these studies.

The patient visits and follow-up including safety laboratories all fall within the SOC follow-up at all sites. These include the biopsies. All clinical standard of care labs and biopsies are followed by clinical operating protocols and are followed by clinical nursing and physician staff.

Study drug:

Exenatide SR

Background.

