- General or specific changes in the patient's condition unacceptable for further treatment in the judgment of the investigator

At the time of withdrawal, all study procedures outlined for the End of Study visit should be completed. The primary reason for a patient's withdrawal from the study is to be recorded in the source documents.

Patients who discontinue treatment will be followed for 30 days to capture possible delayed onset AEs.

Safety reporting plan

Safety will be assessed using incidence of all adverse events (AEs), serious adverse events (SAEs), treatment-emergent adverse events (TEAEs) and AEs leading to study withdrawal; review of laboratory data, including hematology, renal function, biochemistry; new concomitant medication usage; hospitalization rates; and vital signs. Adverse events will be classified for serious adverse events using standard regulatory criteria. Other safety endpoints include the incidence of BK nephropathy, opportunistic infections, and malignancies.

Data Confidentiality

A participant's privacy and confidentiality will be respected throughout the study. Each participant will be assigned a unique identification number and these numbers rather than names will be used to collect, store, and report participant information. Site personnel will not transmit documents containing personal health identifiers (PHI) to the study sponsor or their representatives.

Study Documentation

All clinical data is maintained in Microsoft Excel. All study data is downloaded from this database and stored in tables within a separate Microsoft Access file. Study data is output into study files (xls, jmp, doc, ppt, etc.), which are used for summarizing study information. All active study files are stored within a folder on the Transplant Center research server. The investigator is required to ensure that all clinical data is complete for all participants

Study Coordination

Study coordinators will assist in monitoring participant safety, evaluating the progress of the study, and reviewing procedures for maintaining the confidentiality of data and the quality of data collection, management, and analyses.

Preliminary data:

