We identified 17 kidney transplant recipients who were started on GLP-1 agonists for diabetes in our institution. Discontinuation rate was 17% (similar to non transplant population). Medication was effective in reducing weight, controlling diabetes and decreasing the insulin requirements. Abstract submitted to American Transplant Congress (attached).

Collecting, monitoring and reporting of serious adverse events.

Adverse events will be recorded by PI/co-PI or the care team member in patient medical record using a recognized medical term or diagnosis that accurately reflects the event. Patients will be encouraged to contact care team members by the phone or electronically and reported events will be reviewed by PI/co-PI. Patients will have labs monitored and visits scheduled per standard of care as outlined in the protocol. Additionally, PI/co-PI or designated person on research team will follow up with patient by the phone call or electronically at 7-14 days and 90± 7 days after initiation of drug with open ended questions. Adverse events will be considered based on patient reported symptoms, examinations and laboratory data. Adverse events will be assessed by the investigator for severity, relationship to the investigational product, possible etiologies, and whether the event meets criteria of an SAE and therefore requires immediate notification to AstraZeneca Patient Safety.

Study recording period and follow-up for adverse events and serious adverse events

Adverse events and serious adverse events will be recorded from time of signature of informed consent, throughout the treatment period and including the follow-up period.

All SAEs will be reported, whether or not considered causally related to the investigational product, or to the study procedure(s). The reporting period for SAEs is the period immediately following the time that written informed consent is obtained through 90 days after the last dose of investigational product. The investigators are responsible for informing the Ethics Committee and/or the Regulatory Authority of the SAE as per local requirements.

The investigator will inform the FDA, via a MedWatch form, of any serious or unexpected adverse events that occur in accordance with the reporting obligations of 21 CFR 312.32, and will concurrently forward all such reports to AstraZeneca. A copy of the MedWatch report will be emailed to AstraZeneca (TCS vendor) at the time the event is reported to the FDA.

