Sponsor must also indicate, either in the SAE report or the cover page, the causality of events in relation to all study medications and if the SAE is related to disease progression, as determined by the principal investigator.

PI or co-PI will send SAE report and accompanying cover page by way of email to AstraZeneca's designated mailbox: [REDACTED]

If a non-serious AE becomes serious, this and other relevant follow-up information will be provided to AstraZeneca and the FDA.

Serious adverse events that do not require expedited reporting to the FDA still need to be reported to AstraZeneca preferably using the MedDRA coding language for serious adverse events.

Safety/Tolerability Outcomes Measures:

1. Percentage of Participants with at Least 1 Grade ≥ 2 Treatment Emergent Adverse Event (TEAE) According to Common Terminology Criteria for Adverse Events (CTCAE)

A treatment-emergent adverse event (TEAE) is defined as an adverse event with an onset that occurs after receiving study drug (AE start date greater than or equal to \geq first dose date) and within 30 days after receiving the last dose of study drug (AE start date - last dose date less than or equal to \leq 30). A TEAE may also be a pre-treatment adverse event or a concurrent medical condition diagnosed prior to the date of first dose of study drug, which increases in intensity after the start of dosing.

2. Percentage of Participants with at Least 1 Serious Adverse Event (SAE)

A serious adverse event (SAE) is any untoward medical occurrence or effect that at any dose results in death, is life-threatening, requires inpatient hospitalization or prolongation of existing hospitalization, results in persistent or significant disability / incapacity, is a congenital anomaly / birth defect or is medically important due to other reasons than the above mentioned criteria.

3. Percentage of Participants with at Least 1 Adverse Event Leading to Discontinuation of Investigational Study Medication

Withdrawal due to an AE will occur if the participant experiences an AE that requires early termination because continued participation imposes an unacceptable risk to the participant's health or the participant is unwilling to continue because of the AE.

Safety reporting plan

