The coordinating center will be the primary contact for this study and the data coordinating center: [name] and his program coordinator, M [REDACTED] L [REDACTED] ([REDACTED] and [contact])

1. The FDA investigator-initiated IND will be held by [name]
2. Contracts will preferentially be through the Coordinating Center with subcontracts to the other sites. Indirect costs will be charged only once (i.e. at the site where the funds are actually spent).
3. Protocols will be approved by local IRB (the three Mayo sites have a central IRB).
4. Data is entered into a common database with case-report forms similar to any FDA studies(MEDIDATA Rave case forms specific for transplant are already in place)
5. The Coordinating Center will be responsible for data cleanup, data reporting and reporting to the sponsors and the FDA.
6. Histology:
Mesangial expansion by light microscopy

Schedule of visits

Enrollment Day 122 (4 months)

	Enrollment Day 122 after KTx range 90-180 days	Day 7±3 Days Post enrollment	Monthly labs to 1 year per SOC	Day 90±7	Day 365 ±90 after KTx	Labs q3 months from 12-24 months	Day 730 ± 90 after KTx
Consent	x						
Labs	x	x	x		x	x	x
Clinic visit	x				x		x
Communication through phone call or EMR		x		x		x	
HgbA1c					x	x	x
Biopsy	x				x		x
Pregnancy test	x						

Enrollment Day 365 (1 year)

	Enrollment Day 365 after KTx range 300-420 days	Day 7±3 Days Post enrollment	Labs q 3 months per SOC	Day 90±7	Day 730 ± 90 after KTx
Consent	x				
Labs	x	x	x		x
Clinic visit	x				x
Communication through phone call or EMR		x		x	
HgbA1c					x
Biopsy	x				x
Pregnancy test	x				

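### SAEs are reportable to 90 days after the last exenatide dose, but planned study contact can end at 30 days after withdrawal, or at the final visit for month-24 completers

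*Combined protocol and SAP*

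**What the plan says.** All places are in the combined protocol and SAP.

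- **Study recording period and follow-up for adverse events and serious adverse events:** AEs and SAEs are recorded from consent "throughout the treatment period and including the follow-up period". SAEs, whether or not thought related, are reportable "through 90 days after the last dose of investigational product". The end of the follow-up period is not defined.
- **Stopping Rules (withdrawal text):** "At the time of withdrawal, all study procedures outlined for the End of Study visit should be completed". Then: "Patients who discontinue treatment will be followed for 30 days to capture possible delayed onset AEs".
- **Study design/schedule:** "Patients who discontinued medication for AEs will be contacted within 30 days", to check that symptoms have resolved.
- **Collecting, monitoring and reporting of serious adverse events:** the research team contacts patients at 7–14 days and at 90 ± 7 days after the drug is started. Neither contact is timed from the last dose.
- **Intervention group:** weekly exenatide is to "continue until 24 months post transplant". Use after that is left to the treating physician.
- **Schedule of visits:** the last column of both tables is "Day 730 ± 90 after KTx". Patients enrolled at 4 months also have a quarterly communication between months 12 and 24. Patients enrolled at 12 months have contacts only at Day 7 and Day 90 after enrollment.
- **Safety/Tolerability Outcomes Measures:** the treatment-emergent AE window closes 30 days after the last dose. The percentage of participants with an SAE is listed with no time window.

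**The concern.** The plan sets a 90-day reporting duty after the last dose, but its own follow-up after stopping is 30 days. Its visit schedule can also end on or near the day of the last dose. For part of the reportable period, no one on the study team is scheduled to ask whether an SAE has occurred.

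This matters because safety and tolerability is a secondary objective. The experience cited in kidney recipients is small: a published series of 5 patients on liraglutide and 17 institutional patients on GLP-1 agonists. An unacceptable adverse event is one of the listed reasons for withdrawal, so some patients who leave do so because of a safety problem. Enrollment is to be suspended after two drug-related admissions or a death in the study arm. While enrollment is open, an SAE learned of late could delay that trigger.

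**Working it through.** The plan's only computed figure is the sample size of 81 (54:27). It reproduces with a pooled-variance, two-sided 5% chi-squared calculation at 30% versus 6%: 27 controls, total 81, power 0.802. This point does not alter it. Only the 54 is used below, as a cap on cost.

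**Inputs from the plan:** SAE period ends 90 days after last dose; follow-up after stopping treatment is 30 days; dosing runs to month 24, taken as Day 730; final visit V lies between Day 640 and Day 820 (730 ± 90).

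**1. Exenatide patients who withdraw from the study.** Take withdrawal and last dose as the same day. End of Study procedures are done that day, and follow-up ends 30 days later.

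Reportable days with no planned check = 90 − 30 = **60**, namely post-dose days 31–90.

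If the drug was stopped some time before withdrawal, fewer days remain. The number of such patients is not given. The 17% discontinuation rate under Preliminary data describes diabetic recipients stopping the drug, not patients leaving a study, so it is not used.

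**2. Patients dosed to month 24.** With last dose on Day D and final visit on Day V, days from the final visit to the end of the SAE period = max(0, D + 90 − V).

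| Last dose D | Final visit V | Reportable to | Days left after final visit |
|---|---|---|---|
| 730 | 730 | 820 | **90** |
| 730 | 775 | 820 | 45 |
| 730 | 820 | 820 | 0 |
| 724 | 730 | 814 | 84 |

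The row for Day 724 allows for weekly dosing. A visit on Day 640 with last dose on Day 730 gives 180 by the formula, but only 90 of those days are post-dose. If dosing stops on the day of the final visit (D = V), the result is 90 whatever the visit date.

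If the 30-day rule is read to cover completers too, a last dose on Day 730 gives follow-up to Day 760. The uncovered days become 820 − max(V, 760), at most 820 − 760 = **60**.

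**3. Patients who stop the drug but stay in the study.** A last dose on Day 640 and a visit on Day 730 gives 640 + 90 − 730 = 0. A final visit at least 90 days after the last dose can cover the whole period, so these patients are not part of the gap.

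**The case against.** **Different windows are normal.** A 30-day window for AEs beside a 90-day window for SAEs is common, and the 30 days match the treatment-emergent definition. A reader might infer that the two sections contradict each other. They do not. What is missing is a contact that covers the longer window.

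**Surveillance does not stop.** Transplant recipients stay in close routine care. Labs continue every three months without an end date, clinical staff read them, the care team enters adverse events in the record, and patients are encouraged to report. An admission has a realistic route into the chart. This stands, and it is why a reader should not infer that SAEs are being missed: the documents show no under-count. But these routes are passive. The routine panel (blood count, metabolic panel, tacrolimus) does not ask about an admission elsewhere.

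**Some withdrawn patients cannot be reached.** Withdrawal reasons include patient request and failure to return. This also stands, and it limits the remedy to patients whose consent allows contact or a chart check.

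**The comparison between arms.** A reader might infer that the SAE period is longer on exenatide than on SOC and that the SAE percentage is biased against the drug. The documents do not support this:

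- They give no SAE end date for SOC, and the general recording period is worded the same for everyone.
- The safety outcome list states no comparison between arms and does not say that SAEs in the post-dose tail are counted.
- Even if SOC patients are assumed to be covered to Day 730, the direction is not fixed. A completer enrolled on Day 122 would have 820 − 122 = 698 days against 730 − 122 = 608. A patient who stops 90 days after enrollment would have, on the literal wording, 90 + 90 = 180 days against 608, or against 730 − 365 = 365 for a 12-month enrollee.

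What can be said is narrower: the SOC end date is undefined.

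**Conclusion.** The point holds as a gap between a stated duty and the planned contacts. For exenatide patients who withdraw, 60 of the 90 reportable post-dose days have no planned study check, taking withdrawal and last dose as the same day. For completers with last dose and final visit both on Day 730, the figure is 90 days, or 60 if the 30-day follow-up applies to them. With a last dose on Day 730, it reaches zero only if the visit falls on the last permitted day, Day 820. The completer figures rest on the assumed dose and visit dates. They describe what the schedule permits, not how many patients will be affected.

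The consequence is incomplete assurance of SAE capture. It is not a demonstrated loss of events, and neither power nor the primary endpoint is touched. The missing SOC end date is a secondary point of definition. No size or direction of bias between arms can be claimed from these documents.

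The change is worth making because it is cheap and makes an existing obligation checkable.

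**What to change.** 1. In the withdrawal text under Stopping Rules, change 30 days to 90 days for SAEs. The 30 days can stay for other AEs.
2. In both Schedule of visits tables, add one call or chart check for SAEs at day 90 after the last protocol dose. It applies to exenatide patients who withdraw (where consent allows) or whose last scheduled visit falls less than 90 days after the last dose.
3. Define the last protocol dose as the last dose given by month 24, so that later prescribing by the treating physician does not extend the period indefinitely.
4. State the SAE end date for SOC patients. If SAE percentages are compared between arms, count from randomisation to month 24 in both, and list exenatide SAEs in the post-dose tail separately.

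The cost is a few sentences, one entry in each schedule, and at most 54 brief contacts, one for each planned exenatide patient.

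### Scheduled safety contacts differ between the protocol text and the two visit tables, leaving 12-month entrants about nine months without planned contact and standard-care patients without a contact date in the text

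*Combined protocol and SAP*

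**What the plan says.** Three places set the contact schedule.

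- **Text, Collecting, monitoring and reporting of serious adverse events.** The research team contacts the patient "at 7-14 days and 90± 7 days after initiation of drug with open ended questions". These are the only two contacts in the text, and the only ones said to carry open-ended questions. Otherwise patients are encouraged to report events themselves, and visits and laboratory tests follow standard care.
- **Schedule of visits, table for enrollment at 4 months.** The row "Communication through phone call or EMR" is marked at Day 7, at Day 90 and in the column "Labs q3 months from 12-24 months".
- **Schedule of visits, table for enrollment at 1 year.** The same row is marked at Day 7 and Day 90 only. The column "Labs q 3 months per SOC" has a mark for laboratory tests and none for communication. The next clinic visit is "Day 730 ± 90 after KTx".

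Both tables head the first contact "Day 7±3 Days Post enrollment". The Day 90 column names no starting point. Neither table separates the arms. Under Study design/schedule, the control arm has no study medication, and about half of the patients are to enter at each time point.

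**The concern.** Safety and tolerability of exenatide is a stated secondary objective, and adverse events are to be recorded from consent through treatment and follow-up. How completely non-serious symptoms are captured depends largely on when patients are asked. Two things look wrong.

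1. The two entry cohorts have different contact schedules in the same post-transplant year, on the same weekly drug, and no reason is given. A 12-month entrant has no planned contact for most of the time on study.
2. The text counts contacts from the start of drug and the tables count the first one from enrollment. A site that follows the text has no date on which to call a standard-care patient. In an open-label trial, events would then be asked about in one arm and only volunteered in the other.

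A smaller mismatch is that the window for the first contact differs between text and tables.

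**Working it through.** **Inputs**
- Follow-up: "Patients will be followed for 2 years after transplantation (20 or 12 months after enrollment) for progression to all endpoints" (Study design/schedule).
- Entry for the later cohort: "Enrollment Day 365 after KTx range 300-420 days". Final visit: "Day 730 ± 90 after KTx" (Schedule of visits).
- Second contact: 90±7 days. The table gives no starting point for it; I count from enrollment. The section Intervention group starts drug at randomization, so for exenatide patients the two anchors should nearly coincide.
- Sample size 81, allocated 2:1 (Statistical analysis plan); about 50% enter at 12 months.

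**The plan's own follow-up figures** (month = 365.25/12 days)
- 4-month entrants: 730 − 122 = 608 days = 20.0 months.
- 12-month entrants: 730 − 365 = 365 days = 12.0 months.

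Both agree with the protocol.

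**Gap for 12-month entrants, second contact to final visit**
- Nominal: 365 + 90 = 455; 730 − 455 = 275 days = 9.0 months; 275/365 = 75% of follow-up.
- Entry on Day 365, contact at 90 days, final visit anywhere in its window: 640 − 455 = 185 to 820 − 455 = 365 days.
- All windows, shortest: 640 − (420 + 97) = 123 days.
- All windows, longest: 820 − (300 + 83) = 437 days.

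**Gap for 4-month entrants**
- Nominal: 122 + 90 = 212; 365 − 212 = 153 days = 5.0 months, with monthly laboratory tests.
- Longest within the windows (entry Day 90, contact at 83 days, 12-month visit on Day 455): 455 − (90 + 83) = 282 days.
- From month 12 the table marks communication about every three months.

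**Patients affected**
- 50% of 81 ≈ 40 enter at 12 months. If the 2:1 ratio holds within that cohort, about 27 of them are on exenatide.

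**Anchor and first window**

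| | Text | Tables |
|---|---|---|
| First contact | days 7–14 | days 4–10 |
| Counted from | start of drug | enrollment |
| Date for standard-care patients | none | yes |

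The two windows share days 7–10 only.

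**The case against.** Several stronger readings are tempting, and the documents do not support them.

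- **That 4-month entrants are asked about adverse events every three months.** The row says only that there is communication, in a column headed by laboratory tests. Open-ended questions are attached only to the two contacts in the text, which makes no distinction by entry cohort. On the text alone, neither cohort has a planned adverse-event call after Day 90. What can be shown is a difference in planned contact.
- **That nothing else covers the gap.** Three-monthly laboratory tests continue and are watched by clinical staff. Laboratory findings and examinations count as sources of adverse events, patients can report at any time, and hospitalizations and new medications are reviewed. What is missing is active questioning about symptoms that leave no such trace.
- **That the cohort difference biases the arm comparison.** The tables apply to both arms alike, so the difference does no such harm if the arms are balanced within cohort. The plan does not say that randomization is stratified by entry time, but that does not by itself create a bias. No comparison of adverse-event rates between cohorts is planned.
- **That the arms are certain to be questioned differently.** This follows only if sites use the text in preference to the tables.

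It can also be said that two of the three listed safety measures, treatment-emergent events and discontinuations of study medication, are defined by study drug, and that the third, serious events, depends less on asking. That is fair. However, the Safety reporting plan also lists the incidence of all adverse events, and that is where unequal questioning would show. Early contacts also suit side effects that the background describes as commonly transient. That could justify a front-loaded schedule, but not one that differs by cohort without a reason. Finally, a contact on days 7–10 satisfies both windows, so that mismatch is minor.

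**Conclusion.** The inconsistency is real and should be corrected. About 40 of 81 patients have no planned contact for a nominal 275 days, 75% of their follow-up, with a range of 123 to 437 days over the permitted windows. In that period non-serious symptoms rest on volunteered reports, usual care, three-monthly laboratory tests or recall at the final visit. The 4-month cohort has a shorter gap of its own, 153 days nominally.

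Separately, the text gives standard-care patients no contact date while the tables do. If sites follow the text, non-serious events are solicited in the exenatide arm only, and a between-arm comparison of all-adverse-event incidence would be biased, most plausibly toward more events on exenatide. The size cannot be computed, because the documents give no reporting rates with and without questioning.

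These conclusions assume that the tables are read column by column as they stand, that the Day 90 contact is counted from enrollment, and that the planned equal split by entry time is achieved. The primary endpoint is not touched by this point.

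**What to change.** 1. In the table for enrollment at 1 year, mark the communication row in the three-monthly laboratory column, as the 4-month table already does for months 12 to 24.
2. In Collecting, monitoring and reporting of serious adverse events, count contacts from randomization in both arms instead of from the start of drug, and give the Day 90 column the same anchor.
3. In the same section, state that every scheduled contact, including the three-monthly ones, uses the same open-ended adverse-event questions.
4. Use one window for the first contact in the text and both tables.

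The cost is protocol wording plus about 2 to 3 short phone or portal contacts for each 12-month entrant: 40 × 2 = 80 to 40 × 3 = 120 in all. They can be timed with laboratory tests already drawn, so no visit or test is added. The change concerns only how adverse events are ascertained and leaves treatment as it is.
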